1.1 Primary Objective

Phase I dose finding: To determine the maximum tolerated dose (MTD) of INCB7839 when given in combination with rituximab as consolidation therapy after an autologous hematopoietic cell transplant (HCT) for patients with diffuse large B cell lymphoma (DLBCL)

Phase II expansion phase: To establish a preliminary estimate of progression free survival (PFS) at 6 months post autologous HCT while gaining a more detailed toxicity profile of INCB7839 when administered with rituximab as consolidation therapy

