The primary goal of the dose finding phase is to determine the maximum tolerated dose (MTD) of INCB7839. Up to three dose levels of INCB7839 will be tested (100 mg bid, 200 mg bid, and 300 mg bid). As the 300 mg bid has been proven safe in the non-transplant setting, dose escalation will follow a Fast-Track Design with 1 patient enrolled per dose level until a grade 2 or greater treatment emergent adverse event occurs. A treatment emergent adverse event is any event not present prior to the initiation of the treatment (INCB7839) or any event already present that worsens in either intensity or frequency following exposure to the treatment. At that point, dose escalation will convert to a standard 3+3 design with two additional patients enrolled at the same dose level. If dose level 3 is completed without dose limiting toxicity (DLT) in the 1st 3 patients, an additional 3 patients will be enrolled at this level (without the staggering required by the DLT rules) prior to moving to the phase II component. DLT is defined in section 7.2.2 of the protocol.

Once the phase I dose escalation is completed, an additional 12 patients will be enrolled at the MTD (or dose level 300mg bid, if no DLT) to obtain a more detailed toxicity profile as well as a preliminary estimate of progression free survival at 6 months post-transplant. Persons receiving less than 10 weeks of INCB7839 and/or fewer than 2 doses of rituximab will be replaced for the primary endpoint analysis.

Patients will be followed for 1 year from transplant for progression free survival (PFS) and overall survival (OS).

5 Patient Selection

Study entry is open to patients 18 years and older regardless of gender or ethnic background. While there will be every effort to seek out and include women and minority patients, the patient population is expected to be similar to that of autologous HCT studies at the University Of Minnesota since this is a requirement for study entry.

Inclusion Criteria

- 5.1 Patients 18 years or older who have undergone an autologous HCT for the treatment of DLBCL and are in a complete remission (CR), partial remission (PR) or have stable disease (SD) at the day 28 post-transplant reassessment
- 5.2 Karnofsky Score of $\geq 70\%$ (appendix II)
- 5.3 Able to start the protocol therapy (1st dose of rituximab) between day 28-75 post-transplant
- 5.4 Adequate organ function defined as:

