7.1 Rituximab

Rituximab 375 mg/m² IV will be administered per institutional guidelines at the following time points:

- On (or shortly after) the day 28 post-transplant re-assessment, but no later than post-transplant day 60
- 1 week (+/- 3 days) after the 1st dose
- 7 weeks (+/- 7 days) after the 1st dose

The first dose will be infused over 6 hours. Infusion should start at 50 mg/hour and increase by 50 mg/hour every 30 minutes as tolerated to a maximal infusion rate at 400 mg/hour. If the infusion is well tolerated, the next two doses at 1 and 7 weeks may be administered at 100 mg/hour with 100 mg/hour increments at 30 minutes intervals up to 400 mg/hour.

Premedication: Acetaminophen 650 mg PO and diphenhydramine (e.g. Benadryl) 25 mg PO 30 minutes before each infusion.

Persons receiving fewer than 2 doses of rituximab will be considered unevaluable and replaced.

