7.3 Duration of INCB7839

Patients will take INCB7839 twice a day beginning with the 2nd dose of rituximab and continuing for 90 days (+/- 3 days) unless:

- consent is withdrawn
- patient refuses INCB7839 or is non-compliant
- more than 14 days pass without dosing (regardless of reason), the patient is unable tolerate INCB7839 at the 100 mg bid level or a toxicity recurs (\geq grade 3) after a dose reduction
- disease progression
- unacceptable toxicity
- in the treating physician's medical judgment, continuing with INCB7839 is not in the best interest of the patient's health or well-being

During the extension phase, patients receiving less than 10 weeks of INCB7839 or less than 2 doses of rituximab for reasons other than toxicity will be replaced.

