7.4 Duration of Study Participation

Active study participation will end 1 week after the last dose of INCB7839 unless there is ongoing treatment related toxicity, which will be treated as medically appropriate with follow-up until toxicity resolves to grade 1 or better or is stable for 3 months.

Patients will be seen at 6, 9 and 12 months post-transplant as part of the standard of care follow-up with information regarding disease status and survival recorded for this study unless one of the following occurs:

- consent is withdrawn
- patient is unevaluable – if a patient is not evaluable, follow only until the resolution or stabilization of treatment related toxicity

8 Schedule of Patient Activities

For patient convenience and unnecessary clinic visits; some flexibility is permitted in scheduling study related visits and activities. Through the day 22 visit a window of ± 3 days is permitted. A window of ± 7 days is permitted for the 3rd dose of rituximab. After day 22, visits will coordinate with BMT anniversary visits whenever feasible; however a window of ± 7 days is permitted for any study visits not linked to a BMT anniversary visit. After the end of treatment visit, disease and survival status will be obtained from the BMT database.

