8.1 Standard of Care

Study Time Point	Screening (any time between day +28 and +60))	Day 1 ¹	Day 8	2- 4 days after 2 nd rituximab dose (refer to 8.2)	Day 15	Day 22	Day 36	Day 50	Day 78	End Of Treatment Visit Day 105	F/U for Disease and Survival Status ³
Consent	X										
Medical History	X				X	X	X	X	X	X	
Physical Exam	X				X	X	X	X	X	X	
Height	X										
Weight		X	X					X		X	
Review of transplant related side effects	X										
Karnofsky PS	X				X	X				X	
CBC/diff/plt	X	X	X		X	X	X	X	X	X	
Comprehensive Metabolic panel	X	X	X		X	X	X	X	X	X	
Pregnancy test if applicable	X										
Disease Evaluation ²	X								X		X ³
Rituximab		X	X					X			

1 – day 1 may occur anytime between day 28 and day 75 post-transplant

2 – disease evaluations are the results of the transplant related follow-ups at approximately day +28 and day +100 post-transplant

3 – follow-up after the final treatment visit is linked to transplanted related milestones and/or standard of care visits – information for this study will be obtained from routine data collected by the BMT database

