13.4 Analysis

The primary endpoint of progression free survival (PFS) and the secondary endpoint of overall survival (OS) will be estimated with Kaplan-Meier curves.¹⁵ Cumulative incidence will be used to estimate the probability of relapse/disease progression treating non-relapse death as a competing risk.¹⁶ Safety measures will be measured descriptively with frequencies and proportions.

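### The 10-week replacement rule removes early progressors and early deaths from the primary 6-month PFS estimate, so the estimate can only be biased upward

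*Combined protocol and SAP*

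**What the plan says.** The phase II objective (section 1.1) is "To establish a preliminary estimate of progression free survival (PFS) at 6 months post autologous HCT".

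Three passages deal with replacement:

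- Section 4: "Persons receiving less than 10 weeks of INCB7839 and/or fewer than 2 doses of rituximab will be replaced for the primary endpoint analysis". No reason for short exposure is exempted.
- Section 7.3, which covers the extension only: "patients receiving less than 10 weeks of INCB7839 or less than 2 doses of rituximab for reasons other than toxicity will be replaced". The list of reasons to end INCB7839 in the same section includes disease progression.
- Section 7.1: "Persons receiving fewer than 2 doses of rituximab will be considered unevaluable and replaced".

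On follow-up, section 7.4 says that "if a patient is not evaluable, follow only until the resolution or stabilization of treatment related toxicity". Section 8 says: "After the end of treatment visit, disease and survival status will be obtained from the BMT database". A footnote to the table in section 8.1 says that "disease evaluations are the results of the transplant related follow-ups at approximately day +28 and day +100 post-transplant", although the table marks the on-treatment evaluation at study Day 78.

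Section 13.4 gives the method only: "The primary endpoint of progression free survival (PFS) and the secondary endpoint of overall survival (OS) will be estimated with Kaplan-Meier curves". It names no analysis set and does not say how a patient with short exposure and an early event is handled.

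**The concern.** PFS counts progression and death as failures. A rule that substitutes patients because they stopped early, when progression is itself a reason to stop, selects the primary analysis on its own outcome. Each progressor removed is a known failure. The replacement is either another failure, which leaves the proportion unchanged, or a success, which raises it. No outcome lowers it.

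Early deaths go the same way: all of them under section 4, and those not due to toxicity under section 7.3.

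The study has one arm, so no control group carries the same bias. The result will be read against the 65% in sections 13.1 and 13.3, and section 2.1 says relapse is especially frequent in the first 6 months after transplant.

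Whether a given progressor is removed can also depend on a few days of scheduling. For a day-28 start, a day +100 evaluation falls on study Day 73, which is 65 days after INCB7839 began on Day 8 (under 10 weeks, replaced). The tabulated Day 78 is exactly 70 days (not replaced).

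**Working it through.** **The plan's own figure.** Section 13.3 states 79% power for 18 patients, 65% against 85%, two-sided 0.05, 18 months of accrual and 6 of follow-up. A one-sample log-rank test with exponential PFS reproduces it.

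- Monthly hazards: -ln(0.65)/6 and -ln(0.85)/6. Medians are 9.65 and 25.6 months (stated 9.7 and 25.5).
- Events expected under the alternative: d = 5.89. Events expected under the null hazard over the same follow-up: E = 15.6.
- Power = Phi[(E - d - 1.96 sqrt(E)) / sqrt(d)] = 79.3%.

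This calculation counts events in all 18 patients from the start. It makes no allowance for removing early failures.

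**Timing.** First rituximab is on day e = 28 to 75 (section 5.3). INCB7839 starts a week later (section 4). Ten weeks is reached at m = e + 7 + 70, which is day 105, 127 or 152 for e = 28, 50 or 75. All are before 6 months (182.6 days). Day +100 precedes m for every permitted start.

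**Assumptions for the size.** The drug is inactive. PFS is 65% at 6 months from transplant. S(t) = 0.65^((t/182.6)^k), with k = 1 for constant hazard and k = 0.5 for a declining one. The rule applies to the 12 extension patients, and the 6 phase I patients are unselected. The documents give neither the hazard shape nor the time at which progression is found.

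**Formulas.**

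- No replacement: B = S(182.6)/S(e).
- Replaced, progression found when it occurs: P = S(182.6)/S(m).
- Replaced, progression found only at day +100: D = S(182.6)/S(100).
- Half found promptly, half at study Day 78 and so kept: H = B/(1 - 0.5p), where p = 1 - S(m)/S(e).
- Pooled estimate = (12 x replaced value + 6 x B)/18. Bias = pooled - B.

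**Results, constant hazard (k = 1).**

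| Entry day | B | P | D | Pooled, prompt | Pooled, day +100 | Pooled, half/half |
|---|---|---|---|---|---|---|
| 28 | 0.694 | 0.833 | 0.823 | 0.787 (+9.2) | 0.780 (+8.6) | 0.736 (+4.2) |
| 50 | 0.731 | 0.877 | 0.823 | 0.829 (+9.7) | 0.792 (+6.1) | 0.776 (+4.4) |
| 75 | 0.776 | 0.930 | 0.823 | 0.879 (+10.3) | 0.807 (+3.1) | 0.823 (+4.7) |

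B exceeds 0.65 because a patient must be progression-free to enter. That entry selection is a separate matter and is not counted in the bias.

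Progressors replaced per 12 retained are 12p/(1-p). With prompt detection p = 0.166, giving 2.4. With day +100 detection the share replaced is 0.156, 0.111 or 0.057, giving 2.2, 1.5 or 0.7.

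**Sensitivity (bias in points).**

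| Setting | Prompt | Day +100 |
|---|---|---|
| k = 0.5, 12 of 18 | +7.1 to +8.8 | +2.5 to +8.3 |
| k = 1, rule on all 18 | +13.8 to +15.5 | +4.7 to +12.9 |
| k = 1, 65% counted from entry, 12 of 18 | +10.4 to +15.6 | +4.6 to +9.6 |
| k = 1, 65% counted from entry, all 18 | +15.6 to +23.5 | +6.8 to +14.4 |

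If all progression is first found at study Day 78, after a full 70 days of drug, nobody is replaced for it and the bias is zero.

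**Single-trial illustration.** If 14 of 18 retained patients are progression-free after two early progressors were replaced, the report is 14/18 = 77.8%. With the two counted it is 14/20 = 70.0%.

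**The case against.** The strongest counter-reading is that replacement means extra accrual, not removal. Section 4 does not say excluded or censored, and its next paragraph has patients followed for a year for PFS. Section 7.1 calls only patients with fewer than 2 rituximab doses unevaluable. A patient with under 10 weeks of INCB7839 may therefore still have 6- and 12-month status recorded. This shows that the data may exist, but it does not settle who is analysed. Section 4 ties replacement expressly to the primary endpoint analysis, and no passage returns the replaced patient to it.

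The size does rest on assumptions: hazard shape, detection time, and whether the rule reaches the 6 phase I patients. Only section 7.3 limits it to the extension. The zero end is fragile too. Interruptions of up to 14 days (section 7.2.3) or the 7-day visit window (section 8) can leave a patient short of 70 days of drug at the Day 78 visit. Day 73 and Day 78 may in practice be one evaluation. These points widen the range but do not change the direction.

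It is also fair that the aim is a preliminary estimate from 18 patients; an exact 95% interval around 13/18 is about 47% to 90%. But sampling error is no reason to accept a one-sided bias, and section 13.3 does state a hypothesis test.

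Finally, starting the analysis set at the first rituximab dose goes beyond the patients treated at the designated dose that section 13.2 describes. It adds few events: the chance of one between Day 1 and Day 8 is 1.3% to 2.0%. It is still consistent, because section 7.1 would otherwise remove patients who progress before a second dose.

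**Conclusion.** The concern holds. Under both section 4 and section 7.3, an extension patient who progresses before 10 weeks of INCB7839 is taken out of the primary estimate because of the primary event, so the conclusion does not depend on which section governs. For deaths it does: section 7.3 would keep those whose short exposure was due to toxicity, and section 4 would not.

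On the best-supported reading (PFS counted from transplant, rule on 12 of the 18), the upward bias runs from zero to about 10 points, depending on when progression is found. The top of that range is half of the 20-point difference in section 13.3. Larger values arise only if the rule covers all 18 or the 65% applies from entry. Replacing patients who withdraw or do not comply has no known direction and is not part of this finding. The wording must be corrected before the primary analysis.

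**What to change.** - In sections 4, 7.1, 7.3 and 13.4, define the primary analysis set as every patient assigned to or intended for the phase II dose who receives the first rituximab dose, including those who progress or die before the first INCB7839 dose.
- Count progression or death at any time as a PFS event, and do not replace patients for either in the primary analysis.
- Keep the subset with 10 weeks of INCB7839 and 2 rituximab doses only as a labelled secondary description.
- Reconcile sections 4, 7.1 and 7.3 on patients who stop for toxicity, and state whether the rule applies to the phase I patients counted in the 18.
- In section 7.4, state whether under 10 weeks of INCB7839 makes a patient unevaluable, and that 6- and 12-month disease and survival status is taken from the BMT database for everyone in the primary set unless consent is withdrawn.
- Return any progressors or deaths already replaced to the primary set, and report how many patients were replaced and why.

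The cost is mainly wording. A patient stopped for progression already has an event date, and section 8 already draws later status from the BMT database. Status would have to be retrieved for any patient with fewer than 2 rituximab doses who stopped without an event. The price is a lower PFS estimate that includes some patients with short exposure.

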6.1 Consent and Study Screening in OnCore

Any patient who has been consented is to be entered in OnCore by the Primary Clinical Research Coordinator (PCRC) or designee. If a patient is consented, but not enrolled, the patient's record is updated in OnCore as a screen failure and reason for exclusion recorded.

6.2 Study Enrollment

To be eligible for study enrollment, the patient must sign the treatment consent and meet each of the inclusion criteria and none of the exclusion on the eligibility checklist (Appendix I) based on the eligibility assessment documented in the patient's medical record.

The Primary Clinical Research Coordinator (PCRC) or designee will assign the study treatment arm and add the on-treatment date to complete enrollment.

6.3 INCB7839 Dose Level Assignment

The PCRC or designee will assign each patient to the current dose level of INCB7839 no later than the day of the 2nd rituximab dose.

In March 2016, enrollment to the phase I dose escalation component was completed with INCB7839 at 300 mg twice a day deemed the phase II dose.

6.4 Patients Who Are Registered and Do Not Receive Study Treatment

If a patient is registered to the study, and is later found not able to receive the 1st dose of rituximab by day 75 post-transplant, for whatever reason, the patient will be removed from study and treated at the physician's discretion. The PCRC or designee will update OnCore of the patient's non-treatment status and notify the Principal Investigator. Study data will be collected until the time the patient is off study. The reason for removal from study will be clearly in OnCore. The patient will be replaced to complete enrollment.

7 Treatment Plan

The first dose of rituximab will be considered study week 1 regardless of whether it is given at post-transplant day 28 or as late as post-transplant day 75. Routine post-transplant follow-up will continue as planned, independent of this study, although during active treatment study visits will be scheduled to coincide with transplant related visits (i.e. day 60, 100). Follow-up time points for disease and survival status will remain linked with a post-transplant visit at 6 and 12 months regardless of when the 1st dose of rituximab is given.

7.1 Rituximab

Rituximab 375 mg/m² IV will be administered per institutional guidelines at the following time points:

- On (or shortly after) the day 28 post-transplant re-assessment, but no later than post-transplant day 60
- 1 week (+/- 3 days) after the 1st dose
- 7 weeks (+/- 7 days) after the 1st dose

The first dose will be infused over 6 hours. Infusion should start at 50 mg/hour and increase by 50 mg/hour every 30 minutes as tolerated to a maximal infusion rate at 400 mg/hour. If the infusion is well tolerated, the next two doses at 1 and 7 weeks may be administered at 100 mg/hour with 100 mg/hour increments at 30 minutes intervals up to 400 mg/hour.

Premedication: Acetaminophen 650 mg PO and diphenhydramine (e.g. Benadryl) 25 mg PO 30 minutes before each infusion.

Persons receiving fewer than 2 doses of rituximab will be considered unevaluable and replaced.

7.2 INCB7839

Patients will begin INCB7839 orally at the assigned dose bid the morning of the 2nd rituximab dose and after the research related blood samples are collected. In April 2016 the study moved to the phase II component with the INCB7839 dose set at 300 mg bid. Dose modifications in individual patients are permitted per section 7.2.3.

The tablets are taken twice daily, morning and night, approximately 12 hours apart for 90 days (+/- 3 days) with food.

If the morning or evening dose is missed by more than 4 hours, the patient will skip that dose and take the next scheduled dose at the usual time. Skipped doses will not be made up.

The patient will be provided with a daily drug log to record times of administration, side effects, and missed doses. The patient will be instructed to bring the drug log and study drug bottles (including any empties) to each appointment for reconciliation.

No pre-medications are recommended with the INCB7839 dosing, although side effects may be treated as needed (i.e. acetaminophen for headache, diphenhydramine for nausea).

7.2.1 Supportive Care

In order to provide optimal patient care and to account for individual medical conditions, investigator discretion may be used in the prescribing of all supportive care drug therapy (i.e. anti-emetics, anti-pyretics).

DVT prophylaxis (all patients): On the same day that INCB7839 dosing is started, all patients will begin taking aspirin tablet (325 mg) once a day or on anticoagulant therapy (e.g. warfarin, low-molecular-weight heparin (LMWH) for the duration of INCB7839 administration and for 1 week afterwards as prophylactic measure to reduce the risk of thrombosis.

In the event of “excessive DVT” defined as >20% thrombotic events in patients taking aspirin, all patients (current and future) will be discontinued from aspirin and begin anti-coagulation therapy (e.g. warfarin or LMWH at prophylactic dose) at the time of their next scheduled appointment. Patients within 1 week of discontinuing INCB7839 may continue aspirin as planned.

Serum D-dimer levels will be checked prior to the 1st dose of rituximab, at Day 22, and at the final study visit effective with the April 2016 protocol revision. The frequency was decreased from the phase I monitoring schedule as abnormalities were not seen. If D-dimer level increase >3-fold, than the patient will be considered at high risk of developing DVT/PET and will be switched to warfarin or LMWH for anticoagulation.

7.2.2 INCB7839 Dose Level Assignment

Dose Finding Phase (COMPLETED MARCH 2016)

INCB7839 dose level assignment will occur at the time of study registration based on the following Dose Level cohorts:

Dose Level	INCB7839 Dose (taken twice daily)	Minimum # of Patients*
1	100 mg	1
2	200 mg	1
3	300 mg	6

Initially the Fast Track Design of 1 patient per dose level will be used until a grade 2 or greater treatment emergent adverse event is experienced. At that point, three additional patients will be enrolled at the same dose level and a standard dose escalation design will be used per section 13.2.

Dose Limiting Toxicity is defined as any of the following within the 1st 14 days of INCB7839 dosing:

- any grade 3 or greater non-hematologic, non-infectious toxicity including thromboembolic complications
- selected hematologic toxicity
 - grade 4 neutropenia lasting for ≥ 7 days
 - febrile neutropenia
 - grade 4 thrombocytopenia lasting for ≥ 7 days despite dosing delay
 - grade 3 thrombocytopenia associated with bleeding
- inability to complete at least 20 doses of twice daily INCB7839 therapy within the 1st 14 days due to treatment related toxicity

Dose escalation to the next level cannot proceed until the following conditions are met:

- At least 14 days has passed since the last patient within a dose level began INCB7839
- The maximum tolerated dose (MTD) has not been exceeded

If dose level 3 is reached without DLT in the 1st 3 patients, an additional 3 patients (for a total of 6) will be enrolled without the 14 day waiting period.

Phase II Extension (OPENED TO ENROLLMENT APRIL 2016)

In March 2016 INCB7839 at 300 mg bid was declared the phase II dose level. An additional 12 patients will be enrolled at the MTD established during the phase I component adhering to the early stopping rules found in section 13.4.

